7.2 Study Endpoints

Primary endpoints:

Part A: Signal-to-noise ratio with respect to intra-tumoral hyperpolarized C-13 lac/pyr ratio detected within target liver or other intraabdominal metastasis in patients with advanced solid tumor malignancies.

Part B: Mean percent change from baseline in peak intra-tumoral hyperpolarized lactate/pyruvate ratio after initiation of treatment with PI3K/mTOR pathway inhibitor.

Secondary endpoints

- Frequency of adverse events as graded by Common Toxicity Criteria version 4.0
- Association between percent change from baseline in peak intra-tumoral HP lactate/pyruvate ratio on metabolic MR imaging with subsequent outcomes on PI3K/mTOR pathway inhibitor therapy including clinical benefit rate and progression-free survival (Part B)
- Intra-patient reproducibility of HP lac/pyr ratio for patients who undergo repeated dose imaging studies, as descriptively reported using summary statistics (mean difference, standard deviation, range).

Exploratory endpoint

Association between HP peak lactate/pyruvate signal with immunohistochemical expression level of markers of PI3K/mTOR and glycolytic pathway, including LDH, phosphorylated S6, and phosphorylated Akt. (Part B)

7.3 Sample Size Determination

In Part A of the study, 50 subjects with advanced solid tumor malignancies and at least one metastatic liver or intra-abdominal lesion will undergo hyperpolarized C-13

pyruvate/metabolic MR imaging. The coil arrays will undergo iterative adjustment in geometry and design to optimize the signal-to-noise ratio of intra-tumoral HP lactate/pyruvate.

In Part B of the study, the sample size of 30 evaluable patients is based upon the primary endpoint of this portion of the study, the mean percent change from baseline in peak intratumoral lactate/pyruvate ratio in the target metastatic lesion after initiation of treatment with PI3K/mTOR pathway inhibitor. Assuming the intra-tumoral lactate/pyruvate ratio is 0.80 at baseline and the expected ratio at day 14 is 0.45 (e.g. a 35% decline), based on prior preclinical studies, then a sample size 30 will have > 85% power to detect the significance of the change in signal under paired t-tests with type I error of 5%.

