2.1 Primary Objectives

Part A:

To optimize the signal-to-noise ratio in detecting intra-tumoral hyperpolarized C-13 lactate/pyruvate signal within liver or other intra-abdominal metastases using metabolic MR imaging in patients with advanced solid tumor malignancies.

Part B:

To determine the mean percent change from baseline in peak intra-tumoral hyperpolarized lactate to pyruvate ratio after initiation of treatment with PI3K/mTOR pathway inhibitor.

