7.8.2 Primary Analysis

Descriptive statistics will be used to characterize the mean change from baseline in intratumoral HP pyruvate/lactate ratio for the study cohort, along with 95% confidence interval.

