7.8.3 Analysis of Secondary and Exploratory Endpoints

For the purposes of analyzing the association between percent change from baseline in intratumoral peak lactate/pyruvate ratio on HP MRI with subsequent clinical outcomes, the cohort will be dichotomized by the median percent change. The objective response rate by RECIST 1.1 criteria and clinical benefit rate (response or stable disease for > 24 weeks) will be compared between dichotomized groups using the chi-squared test. The log rank test will be used to compare the radiographic progression-free survival between the two groups.

Safety analyses will be performed for all patients having received a dose of HP C-13 pyruvate. The study will use the NCI CTCAE v4.0.

Analyses will be performed to compare the HP MR markers with immunohistochemical and enzyme expression and activity data from biopsy tissue to investigate the molecular and physiological underpinnings of the HP ¹³C MR data. When both the HP biomarker and molecular biomarker (LDHA activity) are continuous variables, Spearman's rank correlation coefficient will be used to investigate a possible correlation between them. If the outcome is categorical (e.g. immunohistochemistry score 0-1+ vs 2-3+ for pS6, pAkt, LDHA, and MCT 1/4 expression), the HP biomarker distributions will be compared between the two categories using the Mann-Whitney test.

Intra-patient reproducibility of HP lac/pyr ratio for patients who undergo repeated dose imaging studies will be descriptively reported using summary statistics (mean difference, standard deviation, range).

No adjustment will be made for multiple comparisons for the analysis of the secondary and exploratory endpoints.

8 Study Management

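### Section 7.3 calls a fall in the Part B ratio from 0.80 to 0.45 a 35% decline when it is 43.75%, and does not say which figure, or which scale, the power statement rests on

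*Combined protocol and SAP*

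**What the plan says.** Section 7.3 ties the Part B sample size to the primary endpoint: "the sample size of 30 evaluable patients is based upon the primary endpoint of this portion of the study". It then sets the planning effect: "Assuming the intra-tumoral lactate/pyruvate ratio is 0.80 at baseline and the expected ratio at day 14 is 0.45 (e.g. a 35% decline". The sentence goes on: "based on prior preclinical studies, then a sample size 30 will have > 85% power", for a paired t-test with a 5% type I error. It does not say whether the test is one- or two-sided.

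The endpoint is on a relative scale. The Part B objective in section 2.1 reads "To determine the mean percent change from baseline in peak intra-tumoral hyperpolarized lactate to pyruvate ratio", and section 7.2 lists the endpoint as "Mean percent change from baseline in peak intra-tumoral hyperpolarized lactate/pyruvate ratio after initiation of treatment".

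The primary analysis in section 7.8.2 is descriptive: "Descriptive statistics will be used to characterize the mean change from baseline", reported with a 95% confidence interval. That sentence speaks of change, not percent change, and sets no decision threshold.

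No value for an SD appears in the available text. The term occurs only as an output of the same-day reproducibility summary (sections 7.2 and 7.8.3), which "will be descriptively reported using summary statistics (mean difference, standard deviation, range"). Part of the Background around sections 1.2 and 1.3, and the figures, were not available, so an SD there cannot be strictly excluded. Section 7.3 itself gives none and refers to no other section for one.

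**The concern.** The sentence in section 7.3 is the only justification offered for the Part B sample size. It states the planned effect twice, as a pair of ratios and as a percentage, and the two disagree. The figure 35 matches the absolute fall of 0.35, so the likeliest explanation is an absolute difference written as a percentage.

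Because the endpoint is a percent change, a reader will take the percentage as the planned effect on the endpoint's own scale. Someone who later compares the observed mean percent change with the planning value would not know whether that value is 35% or about 44%. The power of a paired t-test depends on the mean change divided by the SD of the change. Here the numerator is ambiguous and the denominator is not given, so the power statement cannot be checked.

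**Working it through.** **Inputs from section 7.3:** baseline ratio 0.80; on-treatment ratio 0.45; label 35%; n = 30 evaluable; paired t-test; type I error 5%; power above 85%. **Not given:** SD of the change, within-patient correlation, sidedness.

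**Step 1. The planning effect.**
- Absolute fall: 0.80 − 0.45 = 0.35.
- Relative fall: 0.35 / 0.80 = 43.75%.
- End ratio for a 35% fall: 0.80 × (1 − 0.35) = 0.52, an absolute fall of 0.28.

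No rounding reconciles 35% with 43.75%.

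**Step 2. The plan's power figure.** It cannot be reproduced, because power needs the SD of the paired change. What can be found is the largest SD at which 30 pairs still give 85% power. From the noncentral t distribution with 29 degrees of freedom and noncentrality (fall / SD) × √30, the required standardized change is 0.566 two-sided or 0.501 one-sided. The SD ceiling is the fall divided by that number.

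| Assumed fall | Two-sided ceiling | One-sided ceiling |
|---|---|---|
| 0.35 (43.75%) | 0.35 / 0.566 = 0.618 | 0.35 / 0.501 = 0.698 |
| 0.28 (35%) | 0.28 / 0.566 = 0.495 | 0.28 / 0.501 = 0.558 |

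On the percent-change scale the two-sided ceilings are about 77 points for a mean change of 43.75% and 62 points for 35%. One-sided they are about 87 and 70 points.

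**Step 3. Power over a range of assumed SDs (two-sided, n = 30).** None of these SDs comes from the documents.

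| SD of paired change | Fall 0.28 | Fall 0.35 |
|---|---|---|
| 0.40 | 96% | 99.6% |
| 0.495 | 85% | 96% |
| 0.55 | 77% | 92% |
| 0.618 | 67% | 85% |
| 0.65 | 63% | 81% |

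The percent-scale ceilings are rough. A percent change in a ratio cannot fall below −100%, and a normal model with mean −35 and SD 62 puts about 15% of patients below that floor. With mean −43.75 and SD 77 it is about 23%.

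**Step 4. Precision.** The planned analysis is an estimate with a 95% confidence interval. The expected half-width is about t(0.975, 29) / √30 × SD = 0.373 × SD. That is 15 points at an SD of 40, 23 at 62 and 29 at 77.

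**Step 5. Is 35% excluded on the endpoint's scale?** No. Take two patients with baselines 1.2 and 0.4 who fall to 0.57 and 0.33. The mean ratios are 0.80 and 0.45. The individual declines are 0.63 / 1.2 = 52.5% and 0.07 / 0.4 = 17.5%, with mean 35%. So group means of 0.80 and 0.45 can coexist with a mean individual decline of 35%. Section 7.3 does not say that this is what it means.

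**The case against.** The strongest reply is that the two ratios are the stated assumption and the percentage is only a parenthetical introduced as an example. Nothing shows that 35% entered the calculation. If the ratios were the inputs, the label has no bearing on the power, and it understates the effect rather than flattering the design. This stands. It rules out saying that the label decides whether the power statement is true. It does not remove the contradiction, because 0.80 to 0.45 is not an example of a 35% decline.

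A second reply is that 35% could be the expected mean of individual percent changes. Step 5 shows that this is possible, so a reader should not infer that 35% is proven wrong on the endpoint's scale. What is established is narrower: the label does not match the ratios beside it, and their relation is not explained.

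A third reply is that the missing SD matters little, since section 7.8.2 is descriptive and no go/no-go decision rests on the power. That also stands. On its own the missing SD is missing detail; it matters here because the effect has to be restated anyway.

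**Conclusion.** Section 7.3 contradicts itself on the Part B planning effect: 43.75% from the ratios against 35% as labelled. This part is exact and needs no assumption. The power claim is unverified, not wrong.

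A reader might infer that Part B is underpowered. For instance, if the unstated SD had been set to give exactly 85% power at 43.75% (about 77 points), power at a true 35% decline would be about 67%, and 46 patients would be needed for 85%. The documents do not support that inference. They give no SD, and they do not show that 35% was the design effect. Power of at least 85% holds under either figure for any SD of the paired change up to about 0.495 two-sided, or 0.558 one-sided. The ceilings assume 30 evaluable pairs and a normal-theory paired t-test. The 95% interval in section 7.8.2 fits a two-sided test, but section 7.3 does not say so. Severity: minor.

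**What to change.** In section 7.3:

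1. Reconcile the effect: about 44% with an end ratio of 0.45; or 35% with an end ratio of 0.52; or an explicit statement that 35% is the expected mean of individual percent changes, with its basis.
2. Restate the power for 30 evaluable pairs on the scale of the primary endpoint, giving the SD with its source and the sidedness used.
3. Add the expected 95% confidence interval half-width, 0.373 × SD, since the primary analysis is an estimate with an interval.

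If no SD from prior work applies, the same-day repeat scans can supply the measurement-error part as a lower bound. That holds only for repeats with the same agent, the same lesion and the same coil and sequence configuration. The repeats are optional (section 5.2), the second injection may use the other labelled pyruvate or cover another region (section 1.4), and coils and sequences change during Part A (section 3.1).

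The cost is a change of wording and one recalculation. N need not change. The restated power may be less favourable than the present figure.

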7.4 Subject Characteristics

Demographic information (e.g. age, race, height, weight, and body mass index) will be summarized using descriptive statistics.

Concurrent medications will be recorded and coded using a standard classification system.

Disease factors for subjects accrued to the study will be characterized using descriptive statistics.

7.5 Replacement Policy

Patients may be replaced in Part B for the following reasons:

- Inability to tolerate/complete imaging scan (with no administration of HP C-13pyruvate)
- Failure of the HP C-13 pyruvate to pass quality control testing, preventing its administration
- Patients who do not undergo subsequent PI3K/mTOR pathway therapy

7.6 Accrual estimates

The study is estimated to accrue approximately 1-2 patients per month leading to an approximate total accrual period of 24 months.

7.7 Interim Analysis

Interim analyses will be conducted for both safety and feasibility. Toxicity will be reviewed on a continuous basis. If at any time (after two or more patients have been accrued) ≥33% of patients experience ≥grade 2 toxicity (excluding asymptomatic laboratory abnormalities deemed to be clinically insignificant by the PI or designee), accrual will be halted for further evaluation.

At the time that it can be determined that continued accrual does not pose significant safety risks to patients accrual may be re-initiated.

Interim analysis for feasibility in Part B will be performed after 33% of patients have been enrolled. Images will be qualitatively reviewed and preliminary data with respect to signal-to-noise ratio within metastatic lesions will be assessed. If it is determined that insufficient signal-to-noise ratio is present to permit analyses of the primary and secondary endpoints, then study accrual will be halted until proper technological adjustments (e.g. alteration of radiofrequency coils, timing from polarization to injection of tracer) have been implemented to ensure higher quality SNR.

7.8 Analytic Plan

7.8.1 Analysis Population

All data from all subjects dosed in the study will be included in all listings, plots, summary tables, and statistical analyses when appropriate. Missing values will not be substituted by estimated values, but treated as missing in the statistical evaluation.

7.8.2 Primary Analysis

Descriptive statistics will be used to characterize the mean change from baseline in intratumoral HP pyruvate/lactate ratio for the study cohort, along with 95% confidence interval.

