Primary Objectives	Part A: To optimize the signal-to-noise ratio in detecting intra-tumoral hyperpolarized C-13 lactate/pyruvate signal within liver or other intra-abdominal metastases using metabolic MR imaging in patients with advanced solid tumor malignancies.			
	Part B: To determine the mean percent change from baseline in peak intra-tumoral hyperpolarized lactate to pyruvate ratio after initiation of treatment with PI3K/mTOR pathway inhibitor.			
Secondary Objectives	To investigate for an association between percent change from baseline in peak intra-tumoral hyperpolarized lactate to pyruvate ratio after initiation of treatment with PI3K/mTOR pathway inhibitor with subsequent clinical outcomes including objective response rate, clinical benefit rate, and progression-free survival. (Part B)			
	To characterize further the safety profile of hyperpolarized C-13 pyruvate injections			
	To determine the reproducibility of intra-tumoral HP lac/pyr ratio with same-day repeated dose studies.			
Exploratory Objective (Part B)	To investigate for an association between intra-tumoral hyperpolarized lactate to pyruvate ratio with histologic markers of PI3K/mTOR pathway and glycolytic metabolism including phosphorylated S6, pAKT, and LDH expression. (Part B; optional)			

[figure not shown]
Study Design

This is a single center prospective imaging study investigating the utility of hyperpolarized C-13 pyruvate/metabolic MR imaging. The current protocol will serve as a companion imaging biomarker study paired with therapeutic trials of PI3K/mTOR pathway inhibitors (e.g. CUDC-907, BYL719), as well as a stand-alone protocol for patients treated with standard-of-care therapies inhibiting the PI3K/mTOR signaling pathway (eg. everolimus).

[figure not shown]
In Part A (run-in feasibility phase), patients will undergo imaging at a single time point, without paired tumor biopsy. There will be no follow up imaging or requirement for treatment with PI3K/mTOR pathway inhibitor. Iterative adjustment of radiofrequency coil geometry and imaging sequences will be undertaken to optimize intra-tumoral hyperpolarized pyruvate/lactate signal-to-noise ratio.

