7.1 Image Processing and Analysis

For each patient, a target metastatic lesion will be selected on the basis of standard imaging (CT or MRI). A region-of-interest (ROI) will be manually drawn in the target lesion, and the same lesion will be evaluated on serial MR scans if the lesion continues to remain evaluable by MRI. If lesion is no longer evaluable on follow up scan, an alternative lesion will be selected on the basis of proximity to original lesion and accessibility by radiofrequency coil for purposes of metabolic MR evaluation.

For the analysis and interpretation of the HP ¹³C MR imaging data, we will utilize the opensource DICOM software package (SIVIC) to align, display and quantitatively interrogate serial multiparametric imaging data. Intra-tumoral ROI will be used to quantify peak HP lactate/pyruvate ratio values in the selected volumes of interest.

In an exploratory fashion, additional metastatic sites in addition to the target lesion will be analyzed and interpreted to determine intra-tumoral peak HP lactate/pyruvate ratio.

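### Section 7.8.2 describes the mean change in pyruvate/lactate, not the Part B endpoint of mean percent change in peak lactate/pyruvate, and Section 7.3 does not settle the scale

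*Combined protocol and SAP*

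**What the plan says.** The Part B target is stated consistently in three places and repeated in a fourth:

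- Abstract, Primary Objectives: "Part B: To determine the mean percent change from baseline in peak intra-tumoral hyperpolarized lactate to pyruvate ratio".
- Section 2.1: "To determine the mean percent change from baseline in peak intra-tumoral hyperpolarized lactate to pyruvate ratio after initiation of treatment with PI3K/mTOR pathway inhibitor".
- Section 7.2: "Part B: Mean percent change from baseline in peak intra-tumoral hyperpolarized lactate/pyruvate ratio after initiation of treatment with PI3K/mTOR pathway inhibitor".
- Section 7.3 names the same percent-change endpoint as the basis for the 30 evaluable Part B patients.

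The measurement and the secondary analysis agree with this. Section 7.1 says: "Intra-tumoral ROI will be used to quantify peak HP lactate/pyruvate ratio values in the selected volumes of interest". Section 7.8.3 relates "percent change from baseline in intratumoral peak lactate/pyruvate ratio on HP MRI with subsequent clinical outcomes".

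Section 7.8.2, the whole of the primary analysis, reads differently: "Descriptive statistics will be used to characterize the mean change from baseline in intratumoral HP pyruvate/lactate ratio for the study cohort". It adds a 95% confidence interval and names no test.

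The planning values are in Section 7.3: "Assuming the intra-tumoral lactate/pyruvate ratio is 0.80 at baseline and the expected ratio at day 14 is 0.45 (e.g. a 35% decline", and then "a sample size 30 will have > 85% power to detect the significance of the change in signal under paired t-tests", at a type I error of 5%. Neither the sidedness nor an SD of the change is given.

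**The concern.** Section 7.8.2 departs from the endpoint in three ways: the ratio is upside down, peak is missing, and percent is missing. The first two can be put right from the rest of the protocol without changing what is estimated. The third cannot be dismissed as easily. A mean change in a ratio and a mean percent change in that ratio are different estimands. Percent change weights each patient by the reciprocal of the baseline value, so patients with low baseline ratios count for more. Part B takes any advanced solid tumor, so baseline ratios may vary widely, although the documents give no distribution.

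A reader would turn to Section 7.3 to settle the scale, but it points both ways. It names percent change, yet it supplies ratio levels and tests a change in signal with paired t-tests. Its percentage label matches the absolute difference. What is at stake is whether the reported primary number is the endpoint the protocol states, and whether the power statement refers to that number.

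**Working it through.** **Inputs.** From Section 7.3: baseline ratio 0.80, follow-up ratio 0.45, n = 30, type I error 5%, power above 85%, paired t-test. Assumed: two-sided testing (one-sided is also shown). The cohorts below are hypothetical, because the documents give no patient-level distribution.

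**1. The planned effect.**

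- Absolute: 0.80 - 0.45 = 0.35.
- Relative: 0.35 / 0.80 = 43.75%, not 35%.
- A true 35% decline would end at 0.80 × 0.65 = 0.52, an absolute change of 0.28.

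**2. Section 7.8.2 read literally.** Taking reciprocals of the group means, pyruvate/lactate goes from 1/0.80 = 1.25 to 1/0.45 = 2.22, a rise of 0.97. This shows only that the expected sign reverses. It is not a forecast, because the mean of reciprocals is not the reciprocal of the mean. The mean pyruvate/lactate change is +0.58 in cohort A below and +8.92 in cohort B.

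**3. With the ratio and peak put right: absolute against percent.** In each cohort half the patients follow each path. Mean baseline is 0.80 and mean follow-up 0.45 throughout.

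| Cohort | Paths | Percent changes | Mean change | Mean percent change |
|---|---|---|---|---|
| A | 1.2 to 0.5; 0.4 to 0.4 | -58.3; 0 | -0.35 | -29.2% |
| B | 1.2 to 0.85; 0.4 to 0.05 | -29.2; -87.5 | -0.35 | -58.3% |
| C | 1.0 to 0.4; 0.6 to 0.5 | -60.0; -16.7 | -0.35 | -38.3% |
| D | 1.0 to 0.7; 0.6 to 0.2 | -30.0; -66.7 | -0.35 | -48.3% |

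The sign can differ too. For 1.6 to 1.2 and 0.2 to 0.3, the changes are -0.4 and +0.1 (mean -0.15), and the percent changes are -25 and +50 (mean +12.5%). This example does not keep the Section 7.3 means; it has 0.90 at baseline and 0.75 at follow-up.

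**4. The power figure.** It cannot be reproduced forward without an SD. Working backward, the power of a paired t-test with n = 30 comes from the noncentral t distribution with 29 degrees of freedom and noncentrality (mean/SD) × √30. Setting power to 85% gives mean/SD = 0.566 two-sided (the normal approximation gives 0.547) and 0.501 one-sided. The largest SD of change compatible with 85% power is the mean divided by that value:

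| Effect intended | Two-sided 5% | One-sided 5% |
|---|---|---|
| 0.35 absolute | 0.35/0.566 = 0.62 | 0.70 |
| 43.75% decline | 43.75/0.566 = 77 points | 87 points |
| 35% decline | 35/0.566 = 62 points | 70 points |

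The choice of effect matters. With an assumed SD of 70 percentage points, two-sided power is 91.1% for a 43.75% decline and 75.4% for a 35% decline.

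**The case against.** The best defense is that the endpoint is not in doubt. The Abstract and Sections 2.1, 7.2 and 7.3 all name percent change in peak lactate/pyruvate, and Sections 7.1 and 7.8.3 fit with it. Section 7.8.2 never says absolute, so its unqualified change could be shorthand for the endpoint in Section 7.2. The inversion looks like loose word order: the Part A signal is written lactate/pyruvate in the objective and pyruvate/lactate in the design text of the Abstract and Section 3.1. Part B is single-arm, the analysis is an estimate with an interval, and no success threshold depends on it.

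Most of this stands. It makes a slip the likely explanation, and it lowers the risk that the scale is chosen after the data are seen, since reporting absolute change alone would visibly depart from Section 7.2. It does not remove the fault. Section 7.8.2 is the only primary-analysis text, nothing overrides it, and the next section does write percent and peak. Absolute change is the natural reading of its words, though not the only possible one.

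The cohorts are also constructed, and the widest range needs a patient falling from 0.4 to 0.05. They show that the scales can diverge, not by how much they will diverge in this trial.

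**Conclusion.** The mismatch is real. Followed as written, Section 7.8.2 reports a different quantity from the Part B endpoint, with the opposite expected sign. With the probable slips corrected, it still most naturally describes an absolute change. At the planning means, a fixed absolute change of -0.35 went with mean percent changes between -29.2% and -58.3% in the examples. The 35% label in Section 7.3 is wrong for 0.80 to 0.45 (43.75%), and the section leaves the scale of the power claim open.

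Two stronger readings are tempting and are not supported. A reader might infer that 30 patients are too few. The documents give no SD, so power above 85% is neither confirmed nor refuted; it holds for any SD below the limits shown, given two-sided 5%. A reader might also infer that the endpoint itself is unsettled or was deliberately replaced. The consistent text elsewhere argues against that.

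This is a specification error in the primary analysis that should be corrected before the data are analyzed. Its consequences are limited by a clear intended endpoint, a descriptive analysis and the absence of a decision rule.

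**What to change.** Replace the text of Section 7.8.2 with:

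> For each Part B patient, P = 100 × (follow-up - baseline)/baseline in the peak intra-tumoral HP lactate/pyruvate ratio of the target lesion. Mean P will be reported with a t-based two-sided 95% confidence interval.

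This leaves the alternate-lesion provisions of Sections 5.5 and 7.1 as they are.

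In Section 7.3, describe 0.80 to 0.45 as an absolute decline of 0.35, or 43.75%. State the scale, the SD and the sidedness on which the power above 85% was computed. If it was computed on absolute change, say so, and do not carry it over to percent change unless that is shown. A log-ratio analysis could be added as a sensitivity analysis, but it is optional.

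The cost is wording in two sections, with no new data and no change of endpoint or sample size. The one downside is that the power statement may have to be requalified or re-derived if it was computed on absolute change or if no SD is on record, and it may then not hold for percent change.
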